### 2.1. PURPOSE OF STUDY

The purpose of the LunulaLaser™ OTC Human Factors Validation Testing is to:

- (i) evaluate the intended user's ability to correctly, safely and effectively set-up, activate and operate the LunulaLaser™ OTC to administer the treatment to the client;
- (ii) evaluate the intended user's ability to understand and apply as applicable the information contained in the LunulaLaser™ OTC Use Device Installation and Proper Use Reference Guide, and device packaging and labeling materials; and
- (iii) identify any and all use difficulties, problems and errors, including those pertaining to critical tasks and close calls demonstrated by intended users during device operation, and to subsequently mitigate each identified instance of use error through device and/or materials modification, and to subsequently evaluate the effectiveness of each modification, as applicable.

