### 4.1. STUDY DESIGN ELEMENTS

The key elements of the study design that support its ability to generalize study results to the intended user under intended use conditions are the following:

- (i) Users (test participants) will represent the intended (actual) users of the LunulaLaser™ OTC; that is, users will be employees at nail salons, beauty salons and spas, fitness and wellness centers, and the like;
- (ii) All critical tasks will be performed, observed and evaluated during the testing;
- (iii) The device user interface and all associated instructional/informational materials will represent the final intended post-clearance (actual use) design; and
- (iv) The simulated-use test conditions will be sufficiently realistic to represent the actual intended conditions of use. Under actual intended conditions of use, the user will receive the Erchonia LunulaLaser™ OTC device in its full packaging via delivery to the facility at which they are employed and will need to rely on the information/instructional information contained in the Installation and Proper Use Reference Guide and the device and packaging labeling to configure and operate the device for use.

(v) In this study, the user will simply be presented with the device in its intended packaging as if receiving it at their place of employment. No additional information, instruction or training will be provided by the Study Observer, or any other individual associated with the study. The user will be left to work out how to operate the Erchonia LunulaLaser™ OTC as independently and naturally as possible without interference or influence from the Study Observer. While the user will have received the instructional information in the packaging as in intended use, he or she will not be instructed to use any of the information. It will be up to the user as to if or how he or she chooses to use that information to set up operation of the device as would occur under actual conditions of intended use.

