#### **6.1.1.2. User Sample Size**

As per the United States Food and Drug Administration (U.S. FDA) document titled ‘Applying Human Factors and Usability Engineering to Medical Devices: Guidance for Industry and Food and Drug Administration Staff’; February 3, 2016, Section 8.1.1 Test Participants (Users), the minimum number of 15 subjects is required to be enrolled in and complete this study. The minimum sample size of 15 subjects is applicable as the intended actual user population in this validation study is a homogenous group of adults who are applicably qualified/licensed/certified/

accredited employees at cosmetology-related facilities such as nail salons, beauty salons and/or spas, fitness and wellness centers, or the like.

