### **6.1.2. CLIENT SAMPLE**

The client sample will be employees of the study sponsor, Erchonia Corporation, who are not involved with the operation of the LunulaLaser OTC, acting as representative clients of the user sample. The acting treatment recipient will be instructed to not provide any insight or feedback during their participation, as if they were an actual client of the user.

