Components that the user attaches to the device, i.e., power cord and key.	
Each of these components and the locations on the LunulaLaser™ OTC to which they are attached/inserted have been designed to be intuitive to determine and easy to locate, access and use. The design took into consideration the design of other similar devices currently on the OTC market. Additionally, the Installation and Proper Use Reference Guide has been clearly designed using both text and related labelled images to demonstrate each step of connection, removal, and operation, as applicable, of each individual component to the device, when and as necessary.

Hardware components to control device operation.	
Following correct attachment of all components to the LunulaLaser™ OTC device, the user operates the device using the key and the icons on the touchscreen on the device interface. The key and the touchscreen placement were designed with consideration of intuitive use and ease of use restricted solely to the tasks the user must perform to safely, and effectively, activate and operate the device. The key is easily inserted into the keyhole and turns without effort to power the device on and off. The

	
icons on the touchscreen are activated by gentle touch with the finger and encompass the Start, Stop, Pause, and Resume icons, and the Time Remaining icon.
 
Each icon activation action is verified by the corresponding result being displayed on the touchscreen. This information is also clearly explained using text and images in the Installation and Proper Use Reference Guide.

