#### **7.2.4. USER USE OF DEVICE**

The user is instructed to operate and use the device to administer treatment to the client following the exact process he or she would follow as if the device had just been received via delivery at his or her place of employment.

As this process is ongoing, the Study Observer will observe the user's performance from opening of the packaged device through to operation and use of the device, or otherwise to as far as the subject is able to complete the process, and will note his or her observations, including observations of use difficulties/problems, errors, and close calls on the Device Use Study Observer Observation Record Form (**Appendix E**).

The Study Observer will not provide any verbal, written or any other form of guidance or assistance to the user throughout this process, and although the Study Observer will record any questions asked by the user during this process, he or she will not answer any questions the user may ask or otherwise interfere in the process, unless intervention becomes necessary for safety reasons.

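### No interruption is scripted in the hands-on session, so a user can pass without using Pause or Resume, and observed evidence on managing an interrupted treatment is left to chance

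*Combined protocol and SAP*

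**What the plan says.** Purpose (i) in Section 2.1 is to evaluate whether the user can "correctly, safely and effectively set-up, activate and operate the LunulaLaser™ OTC to administer the treatment to the client". Section 4.1(ii) adds that "All critical tasks will be performed, observed and evaluated during the testing".

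Section 6.3 describes the interface. The touchscreen icons "encompass the Start, Stop, Pause, and Resume icons, and the Time Remaining icon", and the placement of the key and touchscreen is explained as "restricted solely to the tasks the user must perform to safely, and effectively, activate and operate the device". The same section lists managing the treatment through the touchscreen among the conditions of use, and says that the screen gives information on pausing, resuming and stopping.

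The hands-on session is in Sections 7.2.3 and 7.2.4. After unpacking and setup, "The user is instructed to operate and use the device to administer treatment to the client following the exact process he or she would follow". The observer gives no help and steps in only for safety. The client is a sponsor employee. Under Section 6.1.2, "The acting treatment recipient will be instructed to not provide any insight or feedback during their participation", and this is to be done "as if they were an actual client of the user".

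Section 11.1 makes a user a Study Pass on satisfactory completion of device setup and the treatment procedure. It does not mention interruption. Section 7.1(vi) describes a verbal questionnaire that covers critical tasks, use scenarios and warnings. Section 7.2.6 places it after the user has been asked to read the Guide and labeling. On sample size, Section 6.1.1.2 says that "the minimum number of 15 subjects is required to be enrolled in and complete this study".

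**The concern.** The plan treats pausing, resuming and stopping as part of operating the device, but the session contains nothing that makes a user do any of them early. If the treatment simply runs on, the user can finish and pass with no observed action on Pause or Resume.

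The plan's own description makes interruption foreseeable. Section 6.3 requires correct foot placement, and requires glasses on the client because of a chronic viewing hazard. A client who moves the foot or takes off the glasses undoes one of these during treatment.

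At stake is how a full set of Study Passes would be read. The goal in Section 2 is to show that intended users can use the device without serious errors. Fifteen passes would be taken as support for that, yet might include no observed performance on an interrupted treatment. That part would then rest on verbal answers given after an instructed reading, whereas Sections 4.1(v) and 7.2.3 call it realistic that users choose whether to read the Guide at all.

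**Working it through.** **Coverage, by reading.** These are the steps of Section 7.2, and whether each one requires a user to handle an interruption.

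- 7.2.1 and 7.2.2, consent and eligibility: no.
- 7.2.3, receipt, unpacking and preparation: no.
- 7.2.4, one treatment of a client: none scripted. It may happen by chance.
- 7.2.5, debriefing: verbal.
- 7.2.6, knowledge tasks: verbal, after an instructed reading.

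So the number of users who must perform an interruption task is 0 of 15. The number who happen to do so is unknown.

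**The plan's own figure.** The 15 is taken from cited guidance, with no error rate, power or formula. There is nothing to reproduce, and the point does not dispute it.

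**Size of the gap (illustration).** Inputs:

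- n = 15, from Section 6.1.1.2.
- p, the probability that a user mishandles an interruption when one occurs. This is an assumption, taken as 5%, 10% and 20%.
- q, the share of sessions in which an interruption occurs. This is an assumption, taken as 0, 10% and 100%.

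With users independent, the probability of seeing at least one mishandled interruption is 1 − (1 − q·p)^15.

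| q | p = 5% | p = 10% | p = 20% |
|---|---|---|---|
| 100% (scripted for all) | 53.7% | 79.4% | 96.5% |
| 10% (by chance) | 7.2% | 14.0% | 26.1% |
| 0 (none occurs) | 0% | 0% | 0% |

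For p = 20%:

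- q = 1: 1 − 0.80^15 = 0.965.
- q = 0.10: 1 − 0.98^15 = 0.261.

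At q = 10%, the expected number of users who meet an interruption is 15 × 0.10 = 1.5. The probability that no user meets one is 0.90^15 = 0.206.

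**If no error is seen.** With 15 observed performances and no failures, the one-sided 95% upper limit on the failure rate is 1 − 0.05^(1/15) = 0.181. With no observed performances, the data set no upper limit. The plan analyses its results qualitatively and claims no error rate, so this limit only shows how much information a scripted event would add.

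**The case against.** The best defence has five parts.

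**The client instruction is probably a ban on coaching.** It goes on to say that the person should behave "as if they were an actual client of the user", and a real client may move or ask to stop. A reader might infer that the instruction suppresses interruptions. The documents do not support that: nothing bars a withdrawn foot, removed glasses or a request to stop. The gap does not depend on this reading, because no event is scripted either way.

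**Critical status is unknown.** A reader might infer that Section 4.1(ii) is breached. That promise covers critical tasks only. Section 5.1 defines these by serious harm, and the list is in Appendix A, which is not in the text reviewed. A breach is unproven. If the tasks are critical, the procedure as written does not secure the promise. If they are not, the gap is less serious, but purpose (i) still lacks assured performance data.

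**Section 6.3 is design rationale.** The sentence on required tasks explains where controls are placed. It is not a list of what each participant must do in testing. That is fair. It still shows that the sponsor regards these controls as part of operating the device.

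**Stop may be routine.** A reader might infer that three of the four treatment controls go unused. The Guide in Appendix B, also not in the text reviewed, may call for Stop or even Pause in an ordinary treatment. Neither this nor the run time can be checked.

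**Other evidence exists.** The debriefing and questionnaire cover critical tasks, and the questionnaire covers use scenarios. This stands as evidence of understanding. It does not replace performance by users who chose for themselves whether to read the Guide.

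**Conclusion.** The point holds as a coverage gap. The procedure assures no observed performance on an interrupted treatment, and the pass rule can be met without Pause or Resume. Any such evidence will come from chance interruptions or unprompted use.

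At an assumed 20% mishandling rate, the probability of seeing at least one error is 96.5% if all 15 users meet a scripted event. It is about 26% if an assumed 10% of sessions are interrupted by chance, and 0% if none are. At an assumed 10% mishandling rate, the figures are 79.4%, 14.0% and 0%. The p and q values are illustrative, and the calculation treats users as independent.

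A reader might infer that the study as planned has no chance of detecting such errors. The documents do not support that, because they script no event but rule none out. Appendices E, F and G are also not in the text reviewed, so the actual observation and question items could not be checked. An observer prompt there would conflict with the no-guidance rule in Section 7.2.4. The change is worth making before testing, since afterwards the missing observations would need new sessions.

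**What to change.** In Sections 6.1.2 and 7.2.4, give the acting client a short fixed script with two standard, realistic prompts at set points in the treatment. For example, the client asks to move the foot for a moment, and later asks to stop. Keep the ban on hints about operating the device. The prompts come from the client, so the observer's no-guidance rule is untouched.

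Record each response on the Appendix E form against the Guide's own instructions, and carry any error or close call into the root cause analysis in Section 11.2.1. State whether Appendix A lists these as critical tasks. If it does, count the response in the Section 11.1 pass or fail decision. If not, report it separately.

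The cost is a few minutes per session, a client script and two lines on a form, with no extra people. The prompts make the session slightly less natural than Sections 4.1(v) and 7.2.3 intend, and some users will score worse.

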## **7.2. STUDY PROCEDURE PROTOCOL**

The following procedure protocol will be implemented sequentially and fully for each enrolled user and treatment recipient, as applicable.

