#### **7.2.5. POST-TEST DEBRIEFING INTERVIEW**

Once the user indicates that he or she has completed the device use and treatment application process, the Study Observer will conduct the Post-Test Debriefing Interview (**Appendix F**). The Study Observer will record verbatim the user's responses to each question but will otherwise not react to the user's responses. The Study Observer will not explain or reword any of the questions in the Knowledge Task Patient User Questionnaire and will not provide any guidance or feedback regarding the user's responses in any manner.

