## **8. REGULATORY AND ETHICAL CONSIDERATIONS**

### **8.1. DATA MANAGEMENT**

#### **8.1.1. Data Administration**

For each enrolled user, the Study Observer will be the only individual to record information on the study record forms and only the required data elements will be recorded. There will be no identifying information recorded that could potentially connect an individual user's data record to the individual. Unique de-identified codes will be used on each user's record forms.

The recorded data will only be used for the purposes of evaluating the objectives of this study. The sole parties who will have access to the record forms and the study data will be the Study Observer, the study Sponsor and the study analyst. Access to the record forms and data will not be given to outside parties at any time during the data collation and analysis process or in the future for any reason.

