### **9.2. ADVERSE EVENTS REPORTING**

While it is not anticipated that any adverse events will occur during this Human Factors Validation Testing, any and all potential adverse events observed or reported will be recorded on the applicable record forms and subsequently evaluated and handled in accordance with the study site, IRB and FDA reporting and handling policies and requirements.

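### The client's no-feedback instruction has no safety exception and no later client query is described, so problems only the client can feel may be missed

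*Combined protocol and SAP*

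**What the plan says.** Section 6.1.2 has sponsor employees who do not work with the device play the client. It states: "The acting treatment recipient will be instructed to not provide any insight or feedback during their participation". The reason given is that the client should behave like a real one. No exception is written.

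Section 7.2 says its procedure is to be "implemented sequentially and fully for each enrolled user and treatment recipient, as applicable". The steps that follow gather information from the user only. The debriefing in 7.2.5 begins "Once the user indicates that he or she has completed the device use and treatment application process", and the knowledge questionnaire in 7.2.6 is put to the user. Under 8.1.1, "the Study Observer will be the only individual to record information on the study record forms".

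On safety, section 9.2 commits that "any and all potential adverse events observed or reported will be recorded on the applicable record forms", and it does not limit this to users. Section 7.2.4 lets the observer step in for safety. Section 4.1(ii) states: "All critical tasks will be performed, observed and evaluated during the testing".

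**The concern.** The client wears the glasses and has a foot in the device. Section 5.1 defines a critical task by possible serious harm to the patient as well as to the user, and the client stands in for that patient. The safety-glasses entry in section 6.3 describes a Class 2 laser with a chronic viewing hazard and relies on glasses being correctly fitted to the client.

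Some failures of fitting or positioning may be felt without being visible, for example light leaking past the frame, pressure on the foot, or a symptom. If the client keeps quiet as instructed and nobody asks afterwards, such a problem reaches neither the adverse event record in 9.2 nor the root cause analysis in 11.2.1. The observer may also not learn that the safety intervention allowed in 7.2.4 is needed.

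The plan's aims depend on this information. Section 2.1(iii) sets out to find every use difficulty and error, section 4 claims adequate sensitivity to use errors, and section 5.5.2 says the test can detect errors nobody anticipated.

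**Working it through.** The point is procedural. The plan gives no figure to reproduce, so the check is to trace each route by which a client-side problem could enter the record.

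1. **The client speaks during the session.** Section 6.1.2 tells the client not to give feedback. Its wording covers feedback of any kind, with no safety exception. The safety exceptions in 6.4 and 7.2.4 apply to the observer's conduct, not the client's.
2. **The client is asked afterwards.** Sections 7.2.1 to 7.2.6 cover consent, eligibility, provision of the device, device use, debriefing and knowledge tasks. None collects anything from the client. Section 7.2 mentions the treatment recipient where applicable, but no later step takes this up.
3. **The client completes a form.** Under 8.1.1 only the observer records. Section 7.1 describes the observation form (Appendix E) as covering the user's ability and the debriefing form (Appendix F) as covering the user's perspectives.
4. **The observer sees the problem.** This route is open. Section 6.3 lists glasses fitting and foot placement among the user's operations. Section 7.2.4 has the observer watch from unpacking through use, and section 6.4 requires that observer to be trained on the device.
5. **The client volunteers a report after the session.** The instruction applies during participation, so this is not forbidden. It is also not requested, and no step provides for it.
6. **The analysis draws on client data.** Section 11.2.1 combines observational, knowledge-task and debriefing data. As described in the body, none of these is client testimony.

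The problems then divide as follows:

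| Kind of problem | Route in the plan |
|---|---|
| Visible: glasses not worn, foot misplaced | Observer, under 4.1(ii), 7.2.4 and the observed part of 9.2 |
| Felt only: light in the eyes, discomfort, symptom | No planned route; relies on an unprompted report after the session |

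Section 9.2 covers events that are seen and events that are reported. For the client, the reported part has no planned source, and during the session it meets an instruction pointing the other way.

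Section 6.1.2 also justifies the silence as acting like an actual client. The documents describe no such restriction on an actual client, so the instruction sits awkwardly with 4.1(iv): "The simulated-use test conditions will be sufficiently realistic to represent the actual intended conditions of use".

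**Extent.** Section 6.1.1.2 requires at least 15 users to complete. With one treatment per user, that is 15 × 1 = 15 sessions or more, and the gap is present in each.

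**The case against.** The best case for the plan is that the instruction exists to stop a sponsor employee from coaching the user. That purpose is sound and agrees with the independence rules in 4.1(v) and 7.2.3. The study's target is the user: 2.1(i) and (ii) concern the user's ability and understanding, and 11.1 scores whether the user completes setup and treatment. Section 3 describes the device as nonthermal and non-invasive, and section 6.3 ties eye damage to prolonged direct exposure. A client who announces loose glasses mid-session would also prompt the user on a step under test, and labelling the correction as prompted does not recover what the user would have done alone.

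Most of this stands. The anti-coaching purpose should be kept, and non-urgent remarks about glasses fit should wait until the task is over. It does not close the gap, because a rule against coaching need not cover adverse events, and questions asked after the task cannot cue the user.

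A reader might go further in three ways that the documents do not support:

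- *Client-side problems in general go unrecorded.* They do not. Glasses fitting and foot placement happen in front of a trained observer, and 9.2 also covers observed events.
- *The client is forbidden to report an adverse event or to stop.* Section 6.1.2 mentions neither, and it does not reach beyond the session. The fault is a missing exception and a missing question.
- *It is certain that no form asks the client anything.* The contents of Appendices E and F are not in the text available. The finding rests on how the body describes them.

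**Conclusion.** The concern holds in a limited form. As written, the plan has no planned route for problems that only the client can feel, and 6.1.2 needs to be reconciled with 9.2, with the safety intervention in 7.2.4 and with the aim in 2.1(iii). Visible errors are not affected.

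No rate of missed problems can be given. The documents contain nothing on how often clients feel a problem or how often an observer would notice it. If every problem were visible to the observer, nothing would be lost. A stated percentage of under-counting would be invention.

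The conclusion rests on two assumptions. First, the appendix forms match their description in 7.1. Second, the laser emits during the session; the text has the user administer treatment and does not say that output is disabled. If output were disabled, the light-exposure part would fall away, and fit, foot comfort and other symptoms would remain.

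The matter should be settled before the first session. It bears mainly on adverse event capture and root cause analysis, and less on the pass or fail classification in 11.1.

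**What to change.** 1. **Reword 6.1.2.** The client gives no hints on operating the device and no comment on how the user is performing. State that the no-feedback instruction does not cover adverse events, safety concerns or a wish to stop. Cross-refer to 7.2.4 and 9.2.
2. **Add a short step to 7.2 after the device-use task.** Out of the user's hearing, the observer asks the client a few fixed, neutrally worded questions on glasses fit and light reaching the eyes, comfort of the foot position, and any symptom. The answers go on the observation form (Appendix E).
3. **Protect the test from cueing.** Non-urgent remarks on glasses fit are held for these questions. If a safety remark during the session is followed by a correction from the user, the observer records that correction as client-prompted.
4. **Use the answers.** Name them as a source in 9.2 and 11.2.1.

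The cost is a reworded instruction, a few added lines on an existing form, and an estimated two minutes per session for the existing observer. Over 15 sessions that is 15 × 2 = 30 minutes. The remaining drawback is that, rarely, a genuine safety remark will cue the user; the record will show when that happened.
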